Aim 2: To evaluate changes in iCO, a biomarker of tobacco constituent exposure. *Hyp 2: The degree of change will be directly associated with the degree of substitution with J or NRT—greater levels of substitution will confer a larger decrease in exposure to harmful constituents.*

Aim 3: To evaluate which EC device characteristics and perceived effects influence complete (vs. partial or no substitution). *Hyp 3a: Participants reporting higher product satisfaction, including product durability, battery life, “throat hit”, taste, craving reduction, improved mood with use, and ease of use, will achieve higher rates of complete substitution.*

B. Significance

Quitting is Difficult for Many Smokers

Nearly 50% of smokers make a quit attempt each year, but less than 5% remain abstinent for 3-12 months after quitting.¹⁻³ As a result, the prevalence of cigarette smoking among adults in the U.S. remains disturbingly high.¹ Current cessation products and counseling are effective, doubling a smokers chances of long-term abstinence, but are not universally effective for all smokers, and most smokers fail to quit on their first attempt.⁴⁻⁷ Moreover, a significant minority of smokers finds it very difficult to quit smoking with current FDA-approved products.⁸ To prevent these individuals from returning to smoking following a failed quit-attempt, offering them other less toxic and carcinogenic forms of nicotine would potentially offer a significant health benefit over smoking. This approach is consistent with a tobacco harm reduction model, which asserts that it is preferable to reduce tobacco-related harm by having smokers switch to less toxic products when complete cessation is unobtainable⁹; electronic cigarettes maybe one such product.

The Promise of Electronic Cigarettes: Overview and Limitations of the Available Research

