All participants will be mailed a study smartphone and iCO device, and provided 3 months of unlimited call and data service at no charge and will complete EMAs twice a day for all 12 weeks. Participants will receive one EMA delivered randomly during the day and an evening daily diary (~30 minutes before bedtime). Given the half-life of CO (4-12 hours), we will only request that participants complete iCO measurement for the evening daily diary. Consistent with our team's previous studies, random EMAs will assess: mood, affect, nicotine craving and withdrawal symptoms, stress, recency of vaping/smoking, alcohol use, current setting, and switching self-efficacy; daily diary EMAs will assess conventional cigarettes smoked per day, number of JUUL pods used (if applicable), cigarette/EC satisfaction and pleasure, and measurement of exhaled carbon monoxide with the iCO (see Table 2 for specific EMA measures). All EMAs will be prompted and initiated by the phone. The phone will audibly and visually cue these EMAs for 30 seconds. If the participant has not responded after 3 prompts, the assessment will be recorded as missed. Typically, random sampling assessments take ~1-2 minutes to complete and daily diary assessments take approximately ~3-4 minutes to complete. Participants will be compensated for EMA completion at the 8 and 12 week follow-ups. All assessments will be date and time stamped for future analyses. Participants have the ability to call (e.g., if they have problems completing EMA's) and receive calls from research staff through the smartphone free of charge. The EMA methodology used in this study has been successfully followed by our team as well as other researchers in multiple studies.¹¹⁹⁻¹²⁸ All participants will be sent prepaid mailing boxes and asked to return

Switching to a Vaping Device: Evaluating Risk Reduction among Quitline Treatment Failures

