TLFB		x	x	Cigarette/Vape Availability
Motivation Rulers – 8 to 12		x	x	Cessation Motivation
Cigarette Purchase Task		x	x	Smoking Restriction
iCO		x	x	Vaping Restriction
				Cigarette Reward Value
				Alcohol Use

* Daily Diary EMAs also include Random EMA items

E. Statistical Methods

1. Power Analysis

Complete substitution of combustible cigarettes for EC products is the primary outcome of the study, as the rate of product substitution will likely drive the outcomes for all of the other aims. We will compare the proportion of participants with complete substitution in the JUUL vs. NRT at the end of the product trial phase (8-week follow-up) using the Fisher's exact test. There are no direct data available on which we can base sample size estimates for the proposed study. The closest estimate for the JUUL arm was based on the 6 week, 35% switch rate for JUUL in a pilot study of a community sample of African American/Black smokers ([name], personal communication). Likewise, we estimate that the percent of complete substitution will be 35%. For the NRT, the closest estimate was the 4 week, 30% abstinence rate for preferred NRT product among a sample of smokers motivated to quit smoking¹⁵⁶; however, we will conservatively assume a NRT substitution rate of 20% since participants will have tried NRT previously and were not successful. We will assume an attrition rate of 20%. Assuming 20% attrition among a total of 420 participants (186/group), will allow 300 participants to be analyzed in the final sample. A sample size of 300 will provide >80% power to detect a difference in complete substitution between JUUL and NRT groups for a two-sided .05 level chi-squared test. It is important to note that this sample size is deliberately conservative, as it does not assume the availability of repeated outcome measures that will be taken throughout the study. By choosing models that utilize longitudinal data, we will further increase the power to detect differences between arms

2. Data Analytic Plan

Statistical analyses will be performed using SAS 9.4. P-values less than .05 will be considered statistically significant. Baseline demographics and smoker characteristics will be summarized by groups (JUUL and NRT), as appropriate. Continuous variables will be presented as mean \pm SD and compared among the 2 groups using ANOVA test. Categorical variables will be presented as counts and proportions and compared among the 2 groups using the chi-squared test.

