Switching to a Vaping Device: Evaluating Risk Reduction among Quitline Treatment Failures

Aim 1: The focus of aim 1 is the examination of differential levels of (Hyp 1a) substitution between JUUL and NRT, and (Hyp 1b) reported nicotine craving, withdrawal symptoms, number of cigarettes smoked per day, product abuse liability, and nicotine dependence, between JUUL and NRT. *Hypothesis 1a:* Complete substitution rates, at the 8 and 12 week follow-ups, will be compared between JUUL and NRT arms using logistic regression analysis, adjusting for baseline variables such as age, gender, number of cigarettes per day and/or randomization stratification factors. The GEE model will be performed for the repeated measure analysis of complete substitution rate across multiple visits. *Hypothesis 1b:* If needed, we will apply a normalizing transformation to the response measure (e.g., taking the logarithm of cigarettes per day) before proceeding with the analysis, as a means of removing the effects of potential outliers. We will examine changes in each outcome over time across the two groups using linear mixed model (LMM) regression analysis. We will employ a random intercept or slope parameter, as appropriate, and model the covariance structure for the repeated outcome measures, while accounting for baseline value of the outcome and potential confounders (including any variables not equally distributed between groups). Modeling is done using a likelihood-based approach and thus makes use of all available data (on the intention-to-treat (ITT) sample) to produce consistent estimates of the regression parameters. Contrast estimates comparing group effects over time will be used as measure of effect. A similar approach will be used to explore the EMA data collected.

Aim 2: The focus of aim 2 is the examination of changes in a biomarker of toxicant exposure. *Hypothesis 2:* We will examine changes in iCO, a biomarker of toxicant exposure, and EMA data using the methods outlined in Hypothesis.

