Aim 3: The focus of aim 3 is (Hyp 3a) to determine which EC device characteristics and perceived effects are associated with complete (vs. partial or no) substitution. *Hypothesis 3a:* We will examine whether changes in EC device characteristics and perceived effects obtained by EMA over time differ between those who achieve complete (vs. partial or no) substitution using linear mixed model (LMM) regression analysis. We will employ a random intercept or slope parameter, as appropriate, and model the covariance structure for the repeated outcome measures, while accounting for potential confounders. We will use similar methods to explore return to smoking in those who report complete substitution at any time during the study.

3. Missing Data

In the event of missing data, we will contact participants immediately. If a participant drops out, we will attempt to gather follow-up information by calling the study phone and trying to reach the participant through other provided contact information. However, if a participant refuses to be contacted or loses contact with the investigators, we will censor data at point of loss. Two statistical approaches will be used to handle missing data. First, we will use inverse probability weighting with propensity scores. This is a two-step procedure in which we first model the probability of missingness as a function of baseline covariates and previous outcomes. Next, the inverse of the resulting predicted probabilities (from the logistic regression model) will serve as weights in our proposed model of the response. We will compare these results to a more conservative ITT approach as a final step.

Switching to a Vaping Device: Evaluating Risk Reduction among Quitline Treatment Failures

F. Gender/Minority/Pediatric Inclusion for Research

1. Inclusion of Women and Minorities

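### Hypothesis 3a is about how highly users rate the product, but the only test named for it compares how ratings change over time

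*Combined protocol and SAP*

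**What the plan says.** A. Specific Aims, Aim 3 gives the hypothesis: "Participants reporting higher product satisfaction, including product durability, battery life" and a list of further attributes, "will achieve higher rates of complete substitution". The explanatory side is the level of the rating; the outcome side is the rate of switching.

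E.2 Data Analytic Plan, Aim 3 restates the purpose as "to determine which EC device characteristics and perceived effects are associated with complete (vs. partial or no) substitution". Change over time is not part of that sentence either. The method follows: "We will examine whether changes in EC device characteristics and perceived effects obtained by EMA over time differ between those who achieve complete" substitution and those who do not. The model is a linear mixed model with the rating as the repeated outcome: "We will employ a random intercept or slope parameter, as appropriate, and model the covariance structure for the repeated outcome measures". No average-level or main-effect contrast is named for Hypothesis 3a.

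For the similar model under Hypothesis 1b, E.2 adds: "Contrast estimates comparing group effects over time will be used as measure of effect". The section-wide threshold is "P-values less than .05 will be considered statistically significant". D.3 Measures places "cigarette/EC satisfaction and pleasure" in the daily diary.

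**The concern.** The hypothesis and its test concern different parameters. A difference in change over time says nothing about a difference in level: two groups can rate the product far apart every day for eight weeks and have identical slopes. Conversely, ratings that cross around a common average give different slopes although neither group was more satisfied overall.

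A steady difference is plausible here. Several listed attributes (durability, battery life, ease of use) belong to a fixed device. Table 2 schedules the JUUL Use Evaluation only at +8 and +12 weeks, so that instrument gives no pre-use score to measure change from. The Aim 3 model, unlike that for Hypothesis 1b, mentions no adjustment for a baseline value. Liking that appears in the first days of use therefore sits in the level of the curve, not in its slope.

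If the plan is followed literally, Aim 3 could report a consistently preferred feature as unrelated to switching and a feature with drifting ratings as related. If the analyst turns to the level difference instead, that choice is made after the fact, across many rated items at .05, and E.2 states no adjustment for multiple tests.

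**Working it through.** **Plan's own figure.** The documents give no power or sample size for Hypothesis 3a. E.1 Power Analysis covers only the primary comparison (35% vs 20%, 300 analysed, power above 80%). With 150 per arm and two-sided alpha .05, this reproduces: 83.2% for the chi-squared test and 80.3% for Fisher's exact test. It is used here only for group sizes.

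**Model.** For person i at time t, with G = 1 for complete switchers and time centred:

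rating = b0 + b1·G + b2·t + b3·G·t + (person intercept) + (person slope)·t + error

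- Group difference at time t: b1 + b3·t.
- Difference between groups in change from time s to time u: b3·(u − s). This is the test as worded; its null is b3 = 0.
- Average difference over the phase, time centred: b1. This is the quantity in Hypothesis 3a.
- Steady difference d: b1 = d and b3 = 0. The change test then rejects at alpha, about 5%, for every d. No assumption about SDs is needed for this.

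**Illustration 1, steady difference.** From E.1: 300/2 = 150 analysed JUUL users, 35% switching, 0.35 × 150 = 52.5, taken as 52 vs 98. Assumed: ratings analysed in the JUUL arm only, eight weekly mean ratings, between-person SD 1, residual SD 0.7, random-slope SD 0.08 per week.

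- Variance of a person's mean: 1 + 0.49/8 = 1.061; SD 1.030.
- SE of the group difference: 1.030 × √(1/52 + 1/98) = 1.030 × 0.1716 = 0.177.
- Approximate power of the level test, Φ(d/0.177 − 1.96): 40% at d = 0.3, 81% at 0.5, 99% at 0.8.

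| Steady difference (between-person SD) | Change test, simulated | Level test, simulated |
|---|---|---|
| 0 | 5.0% | 5.0% |
| 0.3 | 5.4% | 40% |
| 0.5 | 4.6% | 79% |
| 0.8 | 4.8% | 99% |

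(4,000 runs per row.) Fitting the mixed model itself at d = 0.5 in 200 runs gave 3.5% for the interaction and 73% for the group main effect; the Monte Carlo SE of the latter is √(0.73 × 0.27/200) = 3.1 points.

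**Illustration 2, the converse.** Assumed: daily ratings for 56 days, 80% completed, between-person and residual SD both 0.7, random-slope SD 0.003 to 0.010 per day, equal average levels, groups drifting apart by 0.2 units over the phase.

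- Slope difference: 0.2/56 = 0.00357 per day.
- Sum of squared centred days: 56 × (56² − 1)/12 = 14,630; × 0.8 = 11,704. Error part of the slope variance: 0.49/11,704 = 0.0000419.
- Random-slope SD 0.003: total SD √(0.0000419 + 0.000009) = 0.00713; SE 0.00122; power Φ(2.92 − 1.96) = 83%.
- Random-slope SD 0.010: total SD √(0.0000419 + 0.0001) = 0.0119; SE 0.00204; power Φ(1.75 − 1.96) = 42%.

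Simulation gave 42–84% for the change test and 4–7% for the level test.

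**The case against.** The strongest reply is that the plan is loosely worded rather than wrong. E.2 never uses the word interaction and states no null hypothesis. Its preceding sentence gives the purpose as association, and a model with group, time and their product also estimates the group difference. Hypothesis 1b is likewise stated in levels and analysed as changes over time, so the phrase may be shorthand for a repeated-measures group comparison. The contrast sentence under Hypothesis 1b, with the remark that EMA data will be explored in a similar way, could cover group differences at successive times. Two listed attributes, less craving and better mood, are themselves worded as changes.

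Much of this stands. A reader might infer that the random intercept removes the level difference, or that the planned model cannot detect it. Neither is right: switching status is a fixed between-person factor, and the random intercept takes up only residual variation around the group means. A reader might also take the simulated rates as forecasts for this trial. They are not: parallel or crossing trajectories were imposed and every SD was assumed.

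The gap in the text remains. The contrast and EMA sentences sit under Aim 1 and name no level contrast for Aim 3; the one question posed for Hypothesis 3a is whether changes differ. That the model could yield the right estimate does not make it the prespecified test.

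**Conclusion.** The point holds as a mismatch between the stated hypothesis and the named test. On the plain reading, a steady difference in ratings leaves the named test rejecting at about 5% whatever its size; this follows from the algebra and needs no assumed SD. The contrast with 40%, 79% and 99% for a level test is illustrative and rests on the assumed SDs, rating schedule and 52/98 split.

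The documents do not support the stronger conclusion that Aim 3 cannot be answered or that its results will be wrong. The data and model suffice, and nothing in the documents shows whether ratings will run parallel, diverge or cross. Aim 3 is not the primary outcome and has no stated power, so the primary comparison is unaffected. The change is still worth making, because the test as written does not address the aim's own question.

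**What to change.** In E.2, Aim 3, replace the sentence that asks whether changes differ with wording such as:

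> For each device characteristic and perceived effect, Hypothesis 3a is tested by the difference in average rating over the product trial phase between participants with complete substitution and all others, estimated as the group main effect in the linear mixed model with time centred. The group-by-time term is reported as a secondary description of trajectories.

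A model of switching with each person's mean rating as predictor should not be treated as interchangeable: it has a different outcome and a different estimand.

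The cost is one sentence and a different contrast from the same model and data. The small downside is that the trajectory comparison becomes secondary. The average over the phase pools ratings given before and after switching, so the result should be reported as association; it does not by itself show that satisfaction came first.

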There remains a lack of prospective and controlled research on the behavioral, toxicological, and physiological effects of electronic cigarettes (ECs) to help the public health community come to a clear and accurate consensus on their risk-benefit. Moreover, the studies that have been completed used various commercially available ECs, e-liquid flavors, and nicotine concentrations, many of which are unavailable today and for which we know very little about, making the generalizability and comparisons between past, present, and future studies very difficult. The present funding opportunity (PAR-17-156) is meant to begin to evaluate, with a high degree of fidelity, ECs as a potential means of reducing smoking-related risks and to provide information on the use and effects of JUUL; it is also meant to do so quickly (two-year study). In order to successfully execute the proposed study, we plan to recruit and enroll recent smoking cessation treatment failures from a state quitline (QL), which predominately serves priority populations (e.g., low socioeconomic status, high levels of mental health conditions). QLs provide ready access to a large number of tobacco users, as well as infrastructure for delivering and testing study interventions quickly. With a two-year time window, QLs are potentially the best real-world platform to quickly and with sufficient statistical power, meaningfully examine smokers' ability and willingness to switch to JUUL, and its impact on their tobacco use behaviors, nicotine dependence, and health. The proposed study will randomly assign 420 smokers who were recent QL treatment failures to JUUL or combination nicotine replacement therapy (NRT). All participants will receive three calls from QL coaches. JUUL and NRT will be provided at no cost for 8 weeks, and the final follow-up will occur 12-weeks post baseline. Our specific aims are to evaluate 1) provision of JUUL vs. NRT on product switching/substitution, craving/withdrawal, abuse liability, number of cigarettes smoked, and perceived nicotine dependence; 2) changes in carbon monoxide (iCO), a biomarker of tobacco constituent exposure; and 3) which EC device characteristics and effects (e.g., satisfaction, "throat hit", craving reduction) influence complete (vs. partial or no) switching.

Project Narrative/relevance to public health:

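### Aim 3 asks whether perceived effects influence complete substitution, but the planned mixed model makes the ratings the response and substitution the group, with no time ordering

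*Combined protocol and SAP*

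**What the plan says.** Section A (Specific Aims) states Aim 3 as: "To evaluate which EC device characteristics and perceived effects influence complete (vs. partial or no substitution". Hypothesis 3a predicts that participants reporting higher satisfaction, on a list that runs from durability and battery life to "ease of use, will achieve higher rates of complete substitution". The Abstract puts the aim in the same direction. In all three places the ratings come first and substitution is the result.

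Section E.2 (Data Analytic Plan, Aim 3) restates the aim more softly: "to determine which EC device characteristics and perceived effects are associated with complete (vs. partial or no) substitution". The analysis then asks whether changes over time in the EMA ratings "differ between those who achieve complete (vs. partial or no) substitution using linear mixed model (LMM) regression analysis". The linear mixed model (LMM) will "model the covariance structure for the repeated outcome measures, while accounting for potential confounders". The EMA ratings are thus the repeated response, and achieved substitution is the grouping variable.

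Three other places bear on timing:

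- Under the EMA and iCO heading in D.3, EMAs run twice daily for all 12 weeks and are date- and time-stamped.
- In D.3 (Measures), complete substitution is a state of at least 7 days, defined from EMA cigarette reports, daily CO and reported e-cigarette use.
- In D.1 and D.2, JUUL participants are asked to try to switch completely for the 8-week product phase, so switching can begin at once.

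**The concern.** The question and the model run in opposite directions. Hypothesis 3a concerns how the rate of substitution changes with ratings. The LMM estimates how ratings differ by substitution status, so no parameter in it answers the hypothesis as worded.

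The second problem is timing. Substitution is reached after randomisation, and ratings are collected both before and after it. Section E.2 does not limit ratings to those given before the switch, does not lag them, and does not say when a participant is classified. If people rate the product higher once they have switched, that rise enters the group difference, and in particular the difference in change over time that the plan sets out to examine. Adjusting for unnamed confounders does not restore time order.

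At stake is the reading of one specific aim: satisfaction that results from switching could be reported as satisfaction that helps bring it about.

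**Working it through.** The documents give no sample size, power or effect size for Aim 3, so there is no figure of the plan's to reproduce. The check has two parts.

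**1. Question and model compared**

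| | Specific Aims, Hyp 3a | E.2, Aim 3 |
|---|---|---|
| Response | Rate of complete substitution | EMA ratings over time |
| Explanatory variable | Perceived effects | Complete vs partial or no substitution |
| Time order | Effects precede substitution | None stated |

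**2. How much a post-switch rise could matter (illustration only)**

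Inputs from section E.1: 300 analysed, so 150 in the JUUL arm; 35% complete substitution. This gives 0.35 × 150 = 52.5 switchers and 97.5 non-switchers on average. Significance is at the plan's 0.05 level, taken as two-sided.

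Assumptions not in the documents: 8 weekly ratings; person SD 1 and residual SD 1; ratings have no effect on switching; switching raises ratings by d from the switch week onward; switch week uniform over weeks 2 to 6, with other timings as a sensitivity check.

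Group-size factor: √(1/52.5 + 1/97.5) = 0.171.

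*Person-mean contrast*, standing in for an LMM group effect:
- SD of a person mean = √(1 + 1/8) = 1.061. SE = 1.061 × 0.171 = 0.182.
- Average share of weeks after the switch = 5/8 = 0.625.
- d = 0.5: shift 0.3125, ratio to SE 1.72, significant in about 40% of trials.
- d = 0.2: shift 0.125, ratio 0.69, about 10%.

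*Slope contrast*, closer to the planned change over time:
- Centred weeks have sum of squares 42. SD of a person slope = 1/√42 = 0.154. SE = 0.154 × 0.171 = 0.0264.
- Switching in week 2, 3, 4, 5 or 6 shifts the slope by d × (3.5, 6, 7.5, 8 or 7.5)/42, on average d × 6.5/42 = 0.155d.
- d = 0.5: shift 0.077, ratio 2.93, about 83%.
- d = 0.2: shift 0.031, ratio 1.17, about 22%.

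Simulation of the same set-up (3,000 trials per cell) agrees to within about one percentage point, with about 5% for both contrasts at d = 0.

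*Sensitivity to timing.* If all switching is at product start, the slope does not shift and that contrast stays at about 5%. The mean shifts by the full d, giving ratios of 0.2/0.182 = 1.10 and 0.5/0.182 = 2.75, or about 19% and 79%. If switching is spread over weeks 1 to 3, the slope contrast at d = 0.5 is about 30%.

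*Would early ratings solve it?* With switching in weeks 2 to 6, a week-1 comparison stays at about 5%. With all switching at product start, week-1 ratings are already post-switch: SE = √2 × 0.171 = 0.242, 0.5/0.242 = 2.07, about 54%. With switching in weeks 1 to 3 it is about 11%. A fixed early window is safe only if those already switched are dealt with.

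**The case against.** Section E.2 says only that effects are associated with substitution. For a test of association, either variable may be placed on the left, and the significant results above are not false positives in that sense, because the simulated ratings do differ by switching status. This stands as far as it goes. A reader might infer that the plan itself claims effects of switching as causes. It does not: the analysis section makes no such claim. The risk comes from setting its result against the wording of the Abstract, Aim 3 and Hypothesis 3a, which is directional.

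A reader might also infer that the plan has chosen to use ratings from the whole period and to classify switching afterwards. Neither is stated. E.2 says only that change over time is examined, and it leaves both the window and the classification time open. The supportable point is that nothing in the plan prevents the two from being mixed.

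Nor should one percentage be quoted as the size of the problem. The results rest on an assumed shift and switch time, and the slope contrast is unaffected if everyone switches at the start.

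Finally, the remedy is not free for every item. Hypothesis 3a names durability, battery life, throat hit, taste and ease of use. The EMA content in D.3 and Table 2 covers satisfaction and pleasure, craving, mood and product information but does not list those five. The JUUL Use Evaluation is scheduled only at +8 and +12 weeks. Items collected only there have no rating that can be shown to precede an earlier switch.

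**Conclusion.** The mismatch is real. Following section E.2 would not estimate what Hypothesis 3a states, and it leaves ratings given before and after switching unseparated. Under the stated assumptions with switching in weeks 2 to 6, a modest post-switch rise of 0.2 to 0.5 yields a significant contrast in about 10% to 40% of trials for person means and 22% to 83% for slopes, although ratings have no influence on switching. With switching at product start the corresponding ranges are about 19% to 79% for means and about 5% for slopes. These figures show that the mechanism can matter; they do not predict the trial's result.

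The point is confined to Aim 3, which is a non-randomised comparison under any model. It should be corrected before analysis.

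**What to change.** Restrict the Aim 3 analysis to the JUUL arm and make complete substitution the outcome, by one of two routes:

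- a discrete-time model (GEE or pooled logistic) of first entry into the qualifying 7-day period, on ratings given before that period starts; or
- a landmark logistic model that excludes, or analyses separately, participants already in a qualifying period at the landmark.

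Adjust for baseline cigarettes per day, baseline dependence and the stratification factors. Logistic and GEE models for substitution are already planned under Hypothesis 1a, and the EMAs are time-stamped, so the tools and much of the data exist.

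The SAP should also:

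- define the rating window and when substitution is classified;
- state how participants who switch at once, and so have no earlier product rating, are handled;
- label as descriptive any Hypothesis 3a item collected only at +8 and +12 weeks;
- keep the planned LMM as a descriptive analysis;
- reconcile the wording of the aim with that of the analysis, and describe the result as observational.

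The cost is SAP wording and modest extra analysis. The downside is that immediate switchers, and items without early ratings, contribute less or nothing to the time-ordered model.
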